## **4.6 Analysis of Efficacy**

### **4.6.1 Primary Analysis**

#### *PROMIS-PI*

The goal of this analysis is to test the efficacy of immersive VR in improving measures of pain interference. The trial will be a success if there is statistical evidence that either immersive VR group is better than sham VR.

The primary efficacy endpoint is the change from study baseline to Day 30 in pain interference as measured by PROMIS-PI t-score. The primary analysis will compare the treatment groups, separately, to the control group using a linear mixed model repeated measures (MMRM) analysis. The repeated measures are the change from baseline PROMIS-PI score obtained at Days 7, 15, 21, and 30, respectively. The model will include fixed categorical effects for treatment, week, treatment by week interaction, and the baseline PROMIS-PI t-score as a continuous covariate. We will employ the Stata *xtmixed* command or the R *lmer* function from the *lme4* package with restricted maximum likelihood estimation (REML) and an unstructured within-patient covariance structure for this model. We will evaluate the assumptions of the model, including normality, using residual and other diagnostic plots of model fit.

From this model, we will estimate least squares means, standard errors, treatment differences in least squares means, and 95% confidence intervals for each time period. Primary inference will be based on the treatment comparison of least squares means for Day 30, and a p-value will be presented for this time period only. The null hypothesis is that the mean difference in the primary endpoint between the treatment groups and the sham control group is zero, versus the alternative hypothesis that these differences are not zero. The hypotheses can be expressed as follows:

$$H_0_a: \mu_{SB} - \mu_{control} = 0 \text{ versus } H_1_a: \mu_{SB} - \mu_{control} \neq 0$$

$$H_0_b: \mu_D - \mu_{control} = 0 \text{ versus } H_1_b: \mu_D - \mu_{control} \neq 0$$

Where  $\mu_{SB}$  refers to the mean change from baseline to Day 30 in Promis-PI t-score in the Skills-based VR treatment group,  $\mu_{control}$  refers to the mean change from baseline to Visit Day 30 in Promis-PI t-score in the sham treatment group, and  $\mu_D$  refers to the mean change from baseline to Day 30 in Promis-PI t-score in the Distraction VR treatment group. The test will be performed using the final MMRM model with a two-sided significance level of 5%. Estimated least squares

means for change from baseline and the observed absolute values ( $\pm$  SE) by treatment group will be plotted over time.

#### 4.6.2 Secondary Analyses

##### *PROMIS-Pain Interference*

The change from study baseline to Day 60 and 90 in Pain Interference as measured by PROMIS-PI is a secondary endpoint. This analysis will compare the treatment groups, separately, to the control group using a MMRM analysis. The repeated measures are the change from baseline PROMIS-PI score obtained for Day 60 and 90, respectively. The model will include fixed categorical effects for treatment, week, treatment by week interaction, and the baseline PROMIS-Pain Interference score as a continuous covariate. We will employ the Stata *xtmixed* command or the R *lmer* function from the *lme4* package with REML and an unstructured within-patient covariance structure for this model. We will evaluate the assumptions of this model, including normality, using residual and other diagnostic plots of model fit.

From this model, we will estimate least squares means, standard errors, treatment differences in least squares means, and 95% confidence intervals for each time point. Primary inference will be based on the treatment comparison of least squares means for Day 90 from this model, and a p-value will be presented for this time period only. The null hypothesis is that the mean difference in the primary endpoint between the experimental arms and the sham arm is zero, versus the alternative hypothesis that this difference is not zero.

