## 1.2 SCHEMA

### 1.3 SCHEDULE OF ACTIVITIES (SOA)

Procedures	Pre-screening	Screening Week Day -8 to -2	Enrollment Day -1 to 0	Day 1 (+ 6 days)	Day 7 (+ 6 days)	Day 15 (+ 6 days)	Day 21 (+ 6 days)	Day 30 (+ 6 days)	Day 45 (+ 6 days)	Day 60 (+ 6 days)	Day 75 (+ 6 days)	Day 90 (+ 6 days)
Prospective patient identified (DEEP 6 or provider registry)	X											
Confirm eligibility and Informed Consent via telephone and REDCap	X											
Online Pain Intensity Journal (7 days)		X										X
Screening Week Online Baseline Survey (see below)		X										
Randomization			X									
Participant receives study intervention kit			X									
Technical onboarding call				X								
Intervention: Participant uses VR therapy program and wears Fitbit Charge 4 watch				X	-----							X
Online survey: NIH HEAL Minimum Dataset	X											X
Immersive Tendency Questionnaire (ITQ)  and Motion Sickness Propensity Survey 	X											
Treatment expectation question	X											
Simulator Sickness Questionnaire (SSQ)  and Presence Survey				X								
Online survey: Primary outcome: PROMIS® Pain Interference	X			X	X	X	X	X	X	X	X	X
Discontinuation of Treatment Questionnaire				X	X	X	X	X	X	X	X	X
PROMIS® Physical Function  , Anxiety  , Depression  , Sleep disturbance  ; Pain intensity/interference with Enjoyment of life/interference with General activity (PEG)  , PCS-6 	X				X		X	X		X	X	X
EMR data: Charlson Comorbidity Index  , CURES and EMR: Prescription Data	X											X
Perceived study arm question, treatments in the last 90 days question												X
Online survey: PHQ-2, GAD-2, PGIC, TAPS [1/2]	X											X
Remote technical support				X	-----							X
End of study procedure question												X

Procedures	Pre-screening	Screening Week Day -8 to -2	Enrollment Day -1 to 0	Day 1 (+ 6 days)	Day 7 (+ 6 days)	Day 15 (+ 6 days)	Day 21 (+ 6 days)	Day 30 (+ 6 days)	Day 45 (+ 6 days)	Day 60 (+ 6 days)	Day 75 (+ 6 days)	Day 90 (+ 6 days)
Event Assessment: AE, SAE and UP review and reporting				X	X	X	X	X	X	X	X	X

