#### 9.4.3 ANALYSIS OF THE SECONDARY ENDPOINT(S)

##### *PROMIS-Pain Interference*

The change from study baseline to Day 60 and 90 in pain interference as measured by PROMIS-Pain Interference is a secondary endpoint. This analysis will compare the treatment groups, separately, to the control group using a MMRM analysis. The repeated measures are the change from baseline PROMIS-Pain Interference score obtained for Day 60 and 90, respectively. The model will include fixed categorical effects for treatment, week, treatment by week interaction, and the baseline PROMIS-Pain Interference score as a continuous covariate. We will employ the Stata *xtmixed* command with REML and an unstructured within-patient covariance structure for this model. We will evaluate the assumptions of the model, including normality, using residual and other diagnostic plots of model fit.

From this model, we will estimate least squares means, standard errors, treatment differences in least squares means, and 95% confidence intervals for each time point. Primary inference will be based on the treatment comparison of least squares means for Day 90, and a p-value will be presented for this time period only. The null hypothesis is that the mean difference in the primary endpoint between the experimental arms and the sham arm is zero, versus the alternative hypothesis that this difference is not zero.

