#### **4.2 Analysis Populations and Patient Disposition**

All efficacy and safety data summaries and analyses will be performed by study arm using an Intent-to-Treat (ITT) population defined as all randomized patients.

The number of patients identified as candidates will be reported, as will the number screened (i.e. consented). The number and percentage of patients randomized, patient population (ITT), and treatment status (completed, discontinued/withdrew) will be summarized both by treatment group and overall. Reasons for discontinuation/withdrawal will be presented.

An exploratory, per protocol (PP) analysis will focus on patients who use the assigned intervention on at least 50% of days during the first 30-day period. Usage meta-data on the headsets will facilitate sample definition in this population.

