##### *PROMIS-Sleep Disturbance*

The change from study baseline to Day 90 in sleep disturbance as measured by PROMIS-Sleep Disturbance is a secondary endpoint. This analysis will compare the treatment groups, separately, to the control group using a MMRM analysis. The repeated measures are the change from baseline PROMIS-Sleep Disturbance score obtained at Days 15, 30, 60, and 90, respectively. The model will include fixed categorical effects for treatment, week, treatment by week interaction, and the baseline PROMIS-Sleep Disturbance score as a continuous covariate. We will employ the Stata *xtmixed* command or the R *lmer* function from the *lme4* package with REML and an unstructured within-patient covariance structure for this model. We will evaluate the assumptions of this model, including normality, using residual and other diagnostic plots of model fit.

From this model, we will estimate least squares means, standard errors, treatment differences in least squares means, and 95% confidence intervals for each time point. Primary inference will be based on the treatment comparison of least squares means for Day 90 from this model, and a p-value will be presented for this time period only. The null hypothesis is that the mean difference in the primary endpoint between the experimental arms and the sham arm is zero, versus the alternative hypothesis that this difference is not zero.

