### *MME*

A key secondary endpoint is the change from study baseline to Day 90 in weekly MME of prescribed medication. Descriptive summary statistics will be presented for weekly MME of prescribed medication at two timepoints: baseline and Day 90. Analysis of this endpoint will compare the difference in weekly MME of prescribed medication between the treatment groups

and control group at baseline and Day 90 using analysis of covariance (ANCOVA), adjusting for baseline MME. We will assess the assumptions underpinning the ANCOVA model graphically and will undertake appropriate transformation of the weekly average MME outcome as deemed appropriate. If no suitable transformations can be found, bootstrapped confidence intervals for the between-group differences in weekly MME will be produced. Both adjusted and unadjusted between-group comparisons will be presented with 95% confidence intervals.

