## **6. GENERAL STATISTICAL/ANALYTIC ISSUES AND APPROACHES**

### **6.1 Handling of Dropouts or Missing Data**

For randomized patients who discontinue early from the study, measurements will not forward to the date of discontinuation. For purposes of analysis, their last day in the study will be the last day on which data was contributed. Unless stated otherwise on a case-by-case basis, no further imputation will be used for descriptive analyses, or for primary and secondary efficacy analyses utilizing MMRM methodology.

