## 6.4 Missing Data and Sensitivity Analyses

If the primary or key secondary endpoint is missing in >15% of patients in either treatment group, then the pattern of baseline covariates with missing values will be examined using the method of Little and in case the data is not missing completely at random, missing values will be imputed using fully conditional specification with the multivariate imputation by chained equations (MICE) algorithm under the missing at random (MAR) assumption. Fifty or so data sets will be generated and analyzed separately, and the results will be combined using the formula according to Van Buuren. Similar considerations will be applied to missing data on the dependent variable in a repeated measure mixed model by investigating patterns of missingness and presence of nonignorable missing response data.

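### The secondary PROMIS Pain Interference model uses only Days 60 and 90, so anyone missing both scores leaves the ITT analysis and the earlier scores go unused

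*SAP*

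**What the plan says.** SAP 4.6.2, under PROMIS-Pain Interference: "The repeated measures are the change from baseline PROMIS-PI score obtained for Day 60 and 90, respectively". Protocol 9.4.3 agrees: "The repeated measures are the change from baseline PROMIS-Pain Interference score obtained for Day 60 and 90, respectively". Both models adjust for baseline, use an unstructured covariance and base inference on Day 90.

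The Protocol 1.3 row "Online survey: Primary outcome: PROMIS® Pain Interference" marks collection at baseline and at Days 7, 15, 21, 30, 45, 60, 75 and 90. As the table reads in the extracted text, Day 1 is marked too.

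The companion models are built differently. For sleep, the SAP has "The repeated measures are the change from baseline PROMIS-Sleep Disturbance score obtained at Days 15, 30, 60, and 90, respectively", and the anxiety and PCS SF-6 models use the same four days.

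The analysis set is the "Intent-to-Treat (ITT) population defined as all randomized patients" (SAP 4.2). On missing data, SAP 6.1 says that "no further imputation will be used for descriptive analyses, or for primary and secondary efficacy analyses utilizing MMRM methodology", unless a case-by-case exception is stated. SAP 6.4 allows multiple imputation under a condition that begins "If the primary or key secondary endpoint is missing in >15% of patients in either treatment group" and also requires that the data are not missing completely at random (MCAR). The only endpoint given the key secondary label is opioid dose: "A key secondary endpoint is the change from study baseline to Day 90 in weekly MME of prescribed medication".

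**The concern.** A likelihood-based repeated-measures model uses a participant only if at least one of the listed responses is observed. Someone with baseline and Days 7 to 45, or with Day 75 alone, but with neither Day 60 nor Day 90, supplies no row. That does not match an analysis set of everyone randomized.

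The larger issue is the assumption behind the estimate. Such a model is valid under missing at random given the data it contains. This one contains baseline and Days 60 and 90. If people leave because of how they felt at Day 21 or Day 30, the scores that explain their leaving are outside the model, so for this model the dropout is not at random. The Day 90 contrast can then be biased, most clearly when the dropout pattern differs between arms.

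Several protocol statements make this more than theoretical. Under Protocol 6.4, a participant who stays silent after the reminders is not approached again until equipment return, so early non-response tends to become loss of both later scores. Protocol 4.1 expects the sham headset to lower control-arm attrition, which concedes that attrition can depend on arm. The amendment history gives, as the reason for the current replacement rule, that dissatisfied users who leave should be counted in the analyses. Here, those who leave before Day 60 are not.

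**Working it through.** **The plan's own figure.** For this scale the plan states 83% power at Day 30: 120 per arm, SD of change √(10² + 10²) = 14.14, difference 5, two-sided 0.025 per comparison, success on either. Simulating that design gives 83.1%. It concerns Day 30 only and is not affected by this point.

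**Who is excluded.** With 360 randomized, 10%, 20% or 30% with neither score means 0.10 × 360 = 36, 0.20 × 360 = 72 or 0.30 × 360 = 108 people outside the model. The SAP 6.4 trigger is 0.15 × 120 = 18 per arm, so the 10% case (12 per arm on average) lies below it. The one hint of scale is Protocol 11.3, which expects half of 360 (180) to be reached at about participant 200: (200 - 180)/200 = 10% replaceable withdrawals. That is not a Day 90 loss rate, and it predates the current replacement rule.

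**Size of bias (assumed inputs).** From the plan: 120 per arm, SD 10, effect -5. Assumed: correlation 0.5 with baseline and 0.6 or 0.7 between visits; loss after Day 30 with log-odds 1.0 per SD of the Day 30 score, worse scores leaving more; half of dropouts still give Day 45. The two-visit analysis regresses Day 90 change on arm and baseline in those with Days 60 and 90. The eight-visit analysis is maximum likelihood with unstructured covariance. There were 1,500 replicates per cell, with Monte Carlo error about 0.03. Each cell shows correlation 0.6, then 0.7.

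| Loss, dropout rule | True effect | Two-visit | Eight-visit |
|---|---|---|---|
| 10%, VR only | -5 | -5.34; -5.48 | -5.02; -5.06 |
| 10%, VR only | 0 | -0.31; -0.40 | 0.02; 0.01 |
| 20%, VR only | -5 | -5.62; -5.74 | -5.01; -4.94 |
| 20%, VR only | 0 | -0.60; -0.76 | 0.01; 0.02 |
| 20%, same rule in all arms | -5 | -4.82; -4.77 | -5.02; -5.01 |
| 20%, same rule in all arms | 0 | 0.02; 0.03 | 0.02; 0.01 |
| 20%, MCAR | -5 | -4.97; -5.01 | -4.98; -5.01 |
| 30%, VR only | -5 | -5.90; -6.20 | -5.03; -5.03 |
| 30%, VR only | 0 | -0.90; -1.14 | 0.00; 0.01 |

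Under MCAR, the SD of the two-visit estimate relative to the eight-visit one is 1.01-1.03 at 10% loss, 1.03-1.06 at 20% and 1.06-1.10 at 30%. A four-visit model (Days 15, 30, 60, 90) at 20% VR-only loss gives -4.99 and -4.97 (null 0.02 and 0.05), so most of the gain needs only the companion models' visit list.

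**Sensitivity.** A separate simulation used one correlation throughout, baseline included, with 1,000 replicates and 12-32% overall loss. Score-dependent dropout in the VR arms moved the two-visit estimate to between -5.20 and -5.72 for correlations 0.3 to 0.7; the all-visit model gave -4.95 to -5.07. At zero correlation neither model was biased. A shallower slope (0.5 per SD, 20% loss) gives -5.2 to -5.3. A steeper one (1.5) gives -5.80 and -6.03.

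**The case against.** The strongest reply is that this is a design choice. The endpoint is change at Days 60 and 90, both documents give a matching model, and anyone with either score stays in. The larger biases need score-dependent dropout in the VR arms only, a mechanism the documents do not describe. With one rule in all arms, the error is about 0.2 points, toward the null, and absent when there is no effect. The SD of the estimate is about 1.0-1.3, so a shift of 0.2-0.4 is a fraction of a standard error. Retention effort is aimed at Day 90 through the compensation schedule (Protocol 5.5) and the follow-up calls and letter (Protocol 7.3). SAP 6.4 also extends its approach to mixed models.

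Much of this stands as a limit on size. The eight-visit model's near-zero bias follows from the simulated mechanism, in which dropout depends only on an observed score. If it depends on later, unobserved pain, both models are biased. Participants with no post-baseline score are lost under either model, so adding visits does not restore the full randomized set. The larger unstructured matrix may not converge, and a misspecified simpler structure could give back some of the protection.

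None of this supplies a reason for leaving out scores already collected. The mixed-model sentence in SAP 6.4 promises to investigate missingness; it names no visits or imputation variables, and it sits beside the no-imputation rule in SAP 6.1.

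**Conclusion.** The concern holds. The textual fact is certain: both documents restrict the responses to two of the collected visits, and no missing-data provision clearly repairs the result. The size is conditional. Under the assumptions above, bias in the Day 90 contrast runs from none (MCAR, or no correlation between visits) through about 0.2 points toward the null (same rule in all arms, 20% loss) to 0.6-0.7 points in favour of VR (VR-only dropout, 20% loss), and up to 1.2 points at 30% loss. In the VR-only case an apparent benefit of 0.6-0.8 points appears at 20% loss where none exists. The precision loss is small. This should be changed before analysis, but it touches a secondary endpoint and leaves the SAP's Day 30 primary analysis intact.

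**What to change.** - In SAP 4.6.2 and Protocol 9.4.3, list Days 7, 15, 21, 30, 45, 60, 75 and 90 as the repeated measures, say whether the Day 1 score is included, and take the Day 60 and Day 90 contrasts from that model. A smaller alternative, matching the companion models, is Days 15, 30, 60 and 90.
- Pre-specify the covariance structure to use if the unstructured one does not converge.
- State in SAP 6.4 whether its imputation rule applies to this endpoint, and reconcile it with SAP 6.1.
- Separately, correct a drafting slip. Protocol 9.4.2 lists Days 7, 15 and 21 but bases inference on Day 30; SAP 4.6.1 and Protocol 9.4.7 include Day 30. Add it.

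The cost is wording and a few lines of code, since the data are already collected. The downside is more covariance parameters, k(k+1)/2: 3 for two visits, 10 for four, 36 for eight, 45 if Day 1 is added. Hence the fallback.

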##### *PROMIS-Sleep Disturbance*

The change from study baseline to Day 90 in sleep disturbance as measured by PROMIS-Sleep Disturbance is a secondary endpoint. This analysis will compare the treatment groups, separately, to the control group using a MMRM analysis. The repeated measures are the change from baseline PROMIS-Sleep Disturbance score obtained at Days 15, 30, 60, and 90, respectively. The model will include fixed categorical effects for treatment, week, treatment by week interaction, and the baseline PROMIS-Sleep Disturbance score as a continuous covariate. We will employ the Stata *xtmixed* command or the R *lmer* function from the *lme4* package with REML and an unstructured within-patient covariance structure for this model. We will evaluate the assumptions of this model, including normality, using residual and other diagnostic plots of model fit.

From this model, we will estimate least squares means, standard errors, treatment differences in least squares means, and 95% confidence intervals for each time point. Primary inference will be based on the treatment comparison of least squares means for Day 90 from this model, and a p-value will be presented for this time period only. The null hypothesis is that the mean difference in the primary endpoint between the experimental arms and the sham arm is zero, versus the alternative hypothesis that this difference is not zero.

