### *PROMIS-Anxiety*

The change from study baseline to Day 90 in anxiety as measured by *PROMIS-Anxiety* is a secondary endpoint. This analysis will compare the treatment groups, separately, to the control group using a MMRM analysis. The repeated measures are the change from baseline *PROMIS-Anxiety* score obtained at Day 15, 30, 60, and 90, respectively. The model will include fixed categorical effects for treatment, week, treatment by week interaction, and the baseline *PROMIS-Anxiety* score as a continuous covariate. We will employ the Stata *xtmixed* command or the R *lmer* function from the *lme4* package with REML and an unstructured within-patient covariance structure for this model. We will evaluate the assumptions of this model, including normality, using residual and other diagnostic plots of model fit.

From this model, we will estimate least squares means, standard errors, treatment differences in least squares means, and 95% confidence intervals for each time point. Primary inference will be based on the treatment comparison of least squares means for Day 90 from this model, and a p-value will be presented for this time period only. The null hypothesis is that the mean difference in the primary endpoint between the experimental arms and the sham arm is zero, versus the alternative hypothesis that this difference is not zero.

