### *PCS SF-6*

The change from study baseline to Day 90 in pain catastrophizing as measured by PCS SF-6 is a secondary endpoint. This analysis will compare the treatment groups, separately, to the control group using a MMRM analysis. The repeated measures are the change from baseline PCS SF-6 score obtained for Day 15, 30, 60, and 90, respectively. The model will include fixed categorical effects for treatment, week, treatment by week interaction, and the baseline PCS SF-6 score as a continuous covariate. We will employ the Stata *xtmixed* command or the R *lmer* function from the *lme4* package with REML and an unstructured within-patient covariance structure for this model. We will evaluate the assumptions of this model, including normality, using residual and other diagnostic plots of model fit.

From this model, we will estimate least squares means, standard errors, treatment differences in least squares means, and 95% confidence intervals for each time point. Primary inference will be based on the treatment comparison of least squares means for Day 90 from this model, and a p-value will be presented for this time period only. The null hypothesis is that the mean difference in the primary endpoint between the experimental arms and the sham arm is zero, versus the alternative hypothesis that this difference is not zero.

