#### 4.6.3 Exploratory Endpoint Analyses

##### PROMIS-PF

The change from study baseline to Day 90 in physical function as measured by PROMIS-PF is an exploratory endpoint. This analysis will compare the treatment groups, separately, to the control group using a MMRM analysis. The repeated measures are the change from baseline PROMIS-PF score obtained for Day 15, 30, 60, and 90, respectively. The model will include fixed categorical effects for treatment, week, treatment by week interaction, and the baseline PROMIS-PF score as a continuous covariate. We will employ the Stata *xtmixed* command or the R *lmer* function from the *lme4* package with REML and an unstructured within-patient covariance structure for this model. We will evaluate the assumptions of this model, including normality, using residual and other diagnostic plots of model fit.

From this model, we will estimate least squares means, standard errors, treatment differences in least squares means, and 95% confidence intervals for each time point. Primary inference will be based on the treatment comparison of least squares means for Day 90 from this model, and a p-value will be presented for this time point only. The null hypothesis is that the mean difference in the primary endpoint between the experimental arms and the sham arm is zero, versus the alternative hypothesis that this difference is not zero.

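### The MMRMs give baseline one slope for all visits although only the last visit is tested; a baseline-by-week term would protect the Day 90 comparisons at almost no cost

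*SAP*

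**What the plan says.** SAP 4.6.2 models change from baseline in sleep disturbance at Days 15, 30, 60 and 90 and describes the mean structure so: "The model will include fixed categorical effects for treatment, week, treatment by week interaction, and the baseline PROMIS-Sleep Disturbance score as a continuous covariate". The covariance is unstructured, fitting is by REML, and the only p-value is for Day 90.

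The other questionnaire models follow the same pattern:
- PCS SF-6: "treatment by week interaction, and the baseline PCS SF-6 score as a continuous covariate".
- Anxiety: the baseline "score as a continuous covariate", with the same four visits.
- Physical function (SAP 4.6.3, exploratory): "treatment by week interaction, and the baseline PROMIS-PF score as a continuous covariate". Depression matches it.
- Pain interference at Days 60 and 90: "and the baseline PROMIS-Pain Interference score as a continuous covariate", with two visits only.
- Primary model (SAP 4.6.1, Days 7 to 30): "treatment by week interaction, and the baseline PROMIS-PI t-score as a continuous covariate".

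None has a baseline-by-week term. Protocol 9.4.2 and 9.4.3 give the same fixed effects. MME is outside the point, because it is analysed "using analysis of covariance (ANCOVA), adjusting for baseline MME".

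**The concern.** The model is flexible everywhere except in the baseline slope. For a change score with equal SDs at all visits, the true slope on baseline at visit t is ρ_t − 1, where ρ_t is the correlation of that visit with baseline. One common slope is right at Day 90 only if ρ is the same at every visit. Otherwise the fit settles on a compromise between the visits, and the Day 90 least-squares means carry the error.

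Two things could follow. The Day 90 comparison is less precise than the same data allow. And where patients leave in a way that depends on baseline and differs by arm, those still observed differ in baseline between arms, so a wrong slope turns that difference into an apparent treatment effect. Such dropout is missing at random given variables already in the model, so a correctly specified MMRM should handle it.

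**Working it through.** **Inputs from the documents.** 120 patients per arm (SAP 3.3). SD 10, stated for PROMIS pain interference (SAP 3.5) and assumed here for the other T-scored scales. Visits and fixed effects as above. The only correlation given is ρ = 0 between baseline and Day 30, used as a conservative sizing value. No correlations by visit and no expected dropout rate are given, so ranges are assumed.

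**1. The plan's own figure.** SD of change = √(10² + 10²) = 14.14. SE = 14.14 × √(2/120) = 1.826, and 5/1.826 = 2.74. One comparison at two-sided 0.025 has about 69% power. Simulating both comparisons against a shared control gives 83.1% for at least one success, against the stated 83%. The inputs are therefore read correctly. This figure does not depend on the baseline slope.

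**2. Precision, complete data.** Let b_t = ρ_t − 1 and let S be the covariance of the visits given baseline, so S90 = 100(1 − ρ90²). The fitted common slope tends to b* = 1′S⁻¹b / 1′S⁻¹1. Then:
- slope per visit: SE = √(2 × S90/120)
- one slope: SE = √(2 × [S90 + 100(b90 − b*)²]/120)

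Example, ρ falling from 0.80 to 0.40: S90 = 84, b90 = −0.600, b* = −0.248. The one-slope variance is 84 + 100 × 0.352² = 96.4, so the SE is 1.268 against 1.183.

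| Assumed ρ, Day 15 to Day 90 | SE, one slope | SE, slope per visit | SE increase | Variance increase |
|---|---|---|---|---|
| 0 throughout | 1.291 | 1.291 | 0% | 0% |
| 0.60 throughout | 1.033 | 1.033 | 0% | 0% |
| 0.65 to 0.55 | 1.081 | 1.078 | 0.2% | about 0.5% |
| 0.70 to 0.50 | 1.132 | 1.118 | 1.2% | about 2.5% |
| 0.80 to 0.40 | 1.268 | 1.183 | 7.1% | about 15% |

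For an illustrative 3-point difference at two-sided 0.05, power goes from 76.5% to 75.5% in the fourth row and from 71.8% to 65.8% in the last.

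The result also depends on the correlation among follow-up visits. With a smoother structure (stable part, exponentially decaying part and error), the variance increase is 2.4% for ρ 0.77 to 0.58, 4.8% for 0.73 to 0.42 and 7.9% for 0.75 to 0.36. Milder decay, to about 0.57, gives 1.5%. The working range is therefore 1.5–8%, with the last table row as an extreme.

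In the two-visit pain interference model the SE rises by 0.0–0.5%. In the primary model the Day 30 variance rises by 0.7–2.4%.

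**3. Bias under dropout.** Both models were fitted by maximum likelihood to 300,000 simulated patients per arm. The true difference was 0, and dropout was logistic in baseline with arm-specific log-odds per SD. The range in each cell runs from nominal 15% to nominal 30% missing. Entries are bias in T-score points with one slope.

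| Assumed ρ | Active 0.5, sham 0 | Active +0.5, sham −0.5 | Active +1, sham −1 |
|---|---|---|---|
| 0.65 to 0.55 | 0.05–0.11 | 0.11–0.22 | 0.17–0.34 |
| 0.70 to 0.50 | 0.16–0.24 | 0.22–0.51 | 0.37–0.73 |
| 0.80 to 0.40 | 0.24–0.51 | 0.48–1.10 | 0.90–1.66 |

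With equal slopes across visits, or with dropout on baseline identical in all arms, there was no bias beyond simulation noise of about 0.05. With a slope per visit, bias was at most about 0.06 in every case.

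The mechanism shows in rough arithmetic: slope error times the baseline gap among those observed at Day 90. For 0.80 to 0.40 with ±0.5 and nominal 30% missing, 0.352 × 3.14 = 1.11, against 1.10 from the fit.

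**4. Size of the test.** In 1,000 simulated trials per scenario (22–23% missing by Day 90, no true effect), the nominal 5% test rejected in 6.8–12.2% with one slope and 5.8–6.6% with a slope per visit.

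**The case against.** A reader might infer that every secondary MMRM loses precision and is biased once dropout differs by arm. The documents do not support that. Both effects need a baseline slope that differs between visits, and nothing in the plan shows one. If the sizing value ρ = 0 held at every visit, the slope would be −1 throughout and the model would be correct. That value is only a conservative bound for Day 30, though, so it does not establish constancy either.

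Other objections also have force:
- The larger bias figures combine steep decay with opposite dropout gradients. The documents do not suggest opposite gradients. Protocol 4.1 discusses attrition in the control arm but not its relation to baseline.
- The error per point of chance baseline imbalance is the same quantity as the precision loss and should not be counted as a second harm.
- The corrected model also rejected slightly above 5%, so not all of the excess comes from the common slope. At 1,000 trials, a rate of 6.8% has a 95% interval of about 5.2–8.4%. The simulations used maximum likelihood, whereas the SAP specifies REML.
- PCS SF-6 is not described as T-scored, so the point figures do not carry over to it.

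SAP 6.4 might be offered as a safeguard, since imputation with regressions specific to each visit could reduce the bias. But its trigger covers the primary and key secondary endpoints, only MME is called key secondary, and SAP 6.1 rules out further imputation for MMRM analyses unless stated case by case. The sentence in SAP 6.4 on mixed-model responses commits to no particular imputation. It is not a clear safeguard for these endpoints.

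**Conclusion.** The omission is certain; its consequence is conditional. If correlation with baseline changes between visits, the four-visit models for sleep, anxiety, PCS SF-6, physical function and depression lose some Day 90 precision. The loss is 0% in variance with flat correlation, about 1.5–8% under assumed moderate to steep decay, and about 15% at 0.80 to 0.40. The primary model is affected less, and the two-visit pain interference model hardly at all.

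If dropout also depends on baseline differently by arm, the bias is roughly 0.2–0.7 T-score points in moderate assumed cases. It exceeds 1 point only with steep decay, opposite gradients and about 26–29% missing. For scale, the Day 90 SE is about 1.1–1.3 and the plan's target difference is 5 points. All correlations and dropout patterns are assumptions. The point is a low-priority improvement that costs almost nothing. It does not demonstrate bias or lost precision in this trial.

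**What to change.** Add a baseline-by-week interaction to the PROMIS and PCS SF-6 MMRMs in SAP 4.6.1, 4.6.2 and 4.6.3 and in Protocol 9.4.2 and 9.4.3. The fixed effects would then be treatment, week, treatment by week, baseline score, and baseline score by week. Leave the Fitbit steps and sleep models outside this change: they use weekly measurements and have no treatment-by-week term, so the same wording would alter them in other ways.

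The cost is three parameters in a four-visit model and one in the two-visit model, with no new data. If the slopes are in fact equal, essentially nothing is lost. The change should be written into both documents before unblinding.
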